**Objectives:**

Specific Aim 1. Evaluate the frequency and clinical features of the metabolic syndrome in childhood cancer survivors.

Hypothesis 1A: Components of the metabolic syndrome are realized in children and adolescents at all stages of therapy of leukemia and lymphomas, can influence the development of complications and late toxic effects.

Hypothesis 1B: Initial health conditions (abnormal IBM, family history, comorbid diseases); drug's toxicity could influence to the appearance of early manifestation of metabolic syndrome.

Specific Aim 2: Evaluate the contribution of functional polymorphisms in candidate genes to metabolic syndrome outcomes among childhood cancer patients.

Hypothesis 2A: Genetic polymorphisms involved in the regulation of the insulin resistance and cancer medications during treatment contribute to the development of metabolic syndrome in childhood cancer survivors.

Specific Aim 3: Assess the extent to which genetic predictors, doses of drugs, risk factors improve the discriminatory performance of standard clinical prediction models for metabolic syndrome outcomes among childhood cancer survivors.

Hypothesis 3 A: Development of metabolic syndrome in cancer patients depends of genetic determinants and toxic effects of antitumor therapy.

Secondary Aim 1: Assess the definition of metabolic syndrome in cohort of patients of leukemia and lymphoma and survivors.

Hypothesis 1A: Episodes of triglyceridemic, insulin resistance (Hyperglycemia, HOMA $>2,7$ , Steroid Diabetes) during the treatment could be the base evidence marker of Metabolic Syndrome in patients treated by antitumor therapy.

Hypothesis 1 B: Endothelial dysfunction as a clinical component of metabolic syndrome is responsible for cardio-vascular abnormalities in cancer survivors.

**Exploratory aim 1:** Assess the association of biomarkers and genetic predictors among childhood cancer survivors with therapeutic exposures (chemotherapy and/or radiation therapy) and metabolic syndrome.

**Evaluation:**

Eligible persons who consent to participate in this trial will be asked to do the following:

- Vital sign measurement including resting heart rate, blood pressure, height, and weight.
- A total of 12 mL of blood will be collected in 3 test tubes. Biomarker analysis will be completed by Laboratory of Dmitry Rogachev National Medical Research Center.
- A Total of 4 mL of blood in 1 test tube will be used for genotyping for the presence of polymorphic variants in genes involved in biotransformation of xenobiotics, insulin resistance and carbohydrate metabolism in the biomolecular laboratory of Dmitry Rogachev National Medical Research Center.
- An echocardiogram and ultrasound will be performed to assess cardiac function.
- CAVI and ABI pulse wave velocity will be non-invasively measured by using the SphygmoCor VaSera VS-1500N. Arterial pressure waveforms will be recorded with a strain gauge pressure sensor placed lightly over the radial artery before and after “6-minutes physical activity”.

**Study Design:** Longitudinal

**Sample Size:** Aims of this study will be accomplished using a longitudinal assessment of 400 patients with ALL/NHL from Dmitry Rogachev National Medical Research Center and other Regional Clinics will be recruiting to the cohort at the start of the therapy MB-ALL/ BFM-NHL. Potentially 2100 survivors ALL/NHL will be treating in “Russkoe Pole” 2018-2021.

**Cases:** Participants for this study will be patients of “Russkoe Pole” cohort (RPC), a longitudinal study designed to evaluate health among children and adolescents survivors of childhood leukemia and lymphoma as they age. Participants in RPC undergo risk-based medical screening according to the Standards of Medical Insurance for rehabilitation of Cancer treated patients. Cases will be stratified by survival time (1-4, 5-9, and  $\geq$  10years).

To be eligible for RPC, cancer survivors must have been treated in Russian children oncology clinics by MB-ALL/ BFM-NHL and be 15 years of age or younger, and at least 6 months from the completion of the therapy. All the patients will have exhaustively full epicrisis of medical history with cumulative doses of medications. Because RPC is a retrospective cohort study with ongoing recruitment (additional survivors become eligible over time).

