**Study Population:**

Eligibility criteria:

- Cancer survivors:
- Treatment with chemotherapy and/or radiation therapy for a primary ALL/NHL diagnosed prior to age 17 years.
- $\leq$  15 years of age at time of enrollment.
- No cytostatic drugs uptake during the study.

Exclusion criteria:

- Diagnosis of diabetes mellitus types 1 or 2 types before antitumor therapy
- Active oncological disease
- History of allogeneic hematopoietic cell transplant
- Absence of written consent for participation from the patient or legally authorized representative

Randomization: N/A
Anticipated Primary Objective Completion Date: 10/09/2018
Anticipated Study Completion Date: 10/12/2021
Analysis of objectives: Aims 1 and 2: Descriptive statistics will be used to summarize prior cancer therapy, collected from formal medical record abstraction. Epidemiological, clinical and laboratory variables, including genetic variants will be tested for their association with metabolic syndrome. McNemar's test for paired data will be used to compare the unmatched general characteristics of cases and controls. Allele frequencies will be estimated by two-side Fisher exact test, and the Chi-square test will be used to check for departures from Hardy-Weinberg equilibrium. Aim 3: The crude disease-exposure association will be determined by estimating the OR and its 95% confidence interval (CI). This will be done by univariate conditional logistic regression, to account for the matched design. The significance of the OR will be assessed by the Wald test. Exposures for which the P-value is less than 0.25 in univariate analysis will be entered into a multivariate conditional logistic regression model. Backward stepwise regression procedures will be used to develop the final multivariate model and possible interactions will be examined. The fit of the model will be assessed by the logistic regression diagnostics procedure. Haplotypes will be constructed where applicable, and pathway analysis will be used to construct multilocus genotypic groups, rather than a "one-gene-at-a-time" approach, where possible. Exploratory Aim: The multiple regression approach as described above (plan for primary Aims 1 and 2) will be implemented to assess the relationship between biomarker levels (HOMA index, triglyceridemic) and endothelial dysfunction (rigidness of arteries and positive biomarkers) with metabolic syndrome in cancer treated patients.

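### The protocol promises a longitudinal study by stage of therapy but fixes matched case-control methods, so frequency by stage and its link to later outcomes are not analysed as written

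*Protocol*

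**What the plan says.** The Evaluation section labels the trial "Study Design: Longitudinal". Its Sample Size entry says the aims will be reached "using a longitudinal assessment of 400 patients", who "will be recruiting to the cohort at the start of the therapy". It then adds a survivor pool: "Potentially 2100 survivors ALL/NHL will be treating in" the rehabilitation centre over 2018-2021. That survivor cohort is described as "a longitudinal study designed to evaluate health among children and adolescents survivors of childhood leukemia and lymphoma as they age", and a few lines later as retrospective.

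Under Objectives, Hypothesis 1A of Specific Aim 1 reads "Components of the metabolic syndrome are realized in children and adolescents at all stages of therapy of leukemia and lymphomas", and goes on to say that these components may affect complications and late toxicity. (The label 1A is used again under Secondary Aim 1; the one meant here is under Specific Aim 1.)

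The Analysis of objectives entry, under Study Population, names methods aim by aim:
- Aims 1 and 2: "Descriptive statistics will be used to summarize prior cancer therapy"; association of epidemiological, clinical, laboratory and genetic variables with metabolic syndrome; McNemar's test for cases against controls; Fisher's exact test for alleles; a chi-square test for Hardy-Weinberg equilibrium.
- Aim 3: crude odds ratios, of which it says "This will be done by univariate conditional logistic regression, to account for the matched design", then a multivariate conditional model with a 0.25 entry threshold and backward selection.
- Exploratory aim: a multiple regression that refers back to the plan for Aims 1 and 2.

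**The concern.** Hypothesis 1A has two parts: how often components occur at each stage of treatment, and whether they precede later complications. Both need records indexed by stage or time within a child, and an analysis that uses the index. The named methods are those of a matched case-control study, in which each child contributes one record as a case or a control. Descriptive statistics are assigned only to the therapy received, not to the frequency of components or of the syndrome.

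At stake is whether the study can answer its first hypothesis from the cohort set up for it. A secondary risk is that an analyst who holds several records per child, with no instruction on how to use them, improvises by choosing one record or by treating all of them as independent.

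**Working it through.** **1. The plan's own figure.** The 400 cannot be reproduced. The protocol gives no alpha, power, effect size, event rate, number of assessments or within-child correlation for it.

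**2. What each question needs, against what the plan assigns.**

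| Question | Needs | Assigned in Analysis of objectives |
|---|---|---|
| Component frequency by stage (Hypothesis 1A) | Proportions by stage, or a model with a stage term | Descriptive statistics for prior therapy only |
| Components preceding later complications (Hypothesis 1A) | Time order within child | Association with the syndrome, no time index |
| Genotype and the syndrome (Aim 2) | One genotype per child; an outcome defined in time if repeated | Fisher and association tests, no time index |
| Predictors of the syndrome (Aim 3) | Outcome time point, or clustering by child | Conditional logistic regression on matched sets |

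The Fisher and Hardy-Weinberg tests properly use one genotype per child and are not at fault. The first two rows have no assigned analysis.

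**3. Could the named methods be turned to repeated records?** McNemar's test can compare two occasions within a child, but the plan assigns it to cases against controls. Conditional logistic regression could take the child as the stratum, but the plan ties it to matched sets. Nor would that rescue the genetic part: genotype is constant within a child, so its main effect drops out of the conditional likelihood.

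**4. Stage-wise frequencies would be informative.** With all 400 children seen at a stage, the 95% half-width of a proportion p is 1.96 × √(p(1−p)/400). The values of p are assumed: 10% gives ±2.9 percentage points, 20% gives ±3.9, 30% gives ±4.5.

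**5. Illustration: what pooling would cost if it were done.** The number of records per child (m) and the within-child correlation (ρ) are assumptions; the protocol gives neither. For an exposure fixed within the child, such as a genotype:
- design effect DE = 1 + (m−1)ρ
- actual type I error = 2 × (1 − Φ(1.96/√DE))
- effective number of independent records = 400m/DE

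For m = 3 and ρ = 0.5: DE = 1 + 2 × 0.5 = 2.0; 1.96/√2.0 = 1.386; type I error 16.6%; coverage of a nominal 95% interval 83.4%.

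| m | ρ | DE | Type I error | Effective records |
|---|---|---|---|---|
| 2 | 0.3 | 1.3 | 8.6% | 615 |
| 2 | 0.7 | 1.7 | 13.3% | 471 |
| 3 | 0.3 | 1.6 | 12.1% | 750 |
| 3 | 0.5 | 2.0 | 16.6% | 600 |
| 3 | 0.7 | 2.4 | 20.6% | 500 |
| 4 | 0.3 | 1.9 | 15.5% | 842 |
| 4 | 0.5 | 2.5 | 21.5% | 640 |
| 4 | 0.7 | 3.1 | 26.6% | 516 |

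A simulation (400 children, assumed 30% carriers, assumed 20% prevalence, 4000 runs per setting) gave 12.6% and 16.0% for m = 3 at ρ = 0.3 and 0.5, and 14.9% and 22.1% for m = 4, close to the formula. With one record per child the test size is right, on 400 records.

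**6. The population.** The only eligibility criteria listed are for survivors. They bar cytostatic treatment on study and exclude active cancer. The 400 are enrolled as treatment begins. Read literally, the children needed for Hypothesis 1A do not meet the criteria.

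**The case against.** The strongest reply is that a longitudinal cohort does not oblige a longitudinal model. Follow-up can serve to establish one outcome per child, with earlier exposures as predictors, and a case-control comparison nested in a cohort is a recognised design. Several aims concern outcomes in survivors, where one endpoint per child may be enough. For Aims 1 and 2 the association model is not named, covariates are not listed and interactions are to be examined, so an SAP has room to add detail.

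Much of this stands. It shows that one record per child is acceptable for some aims, and that the choice between GEE, a mixed model and a hazard model is partly preference. It does not supply an analysis of frequency by stage. Nor is the gap simply left to an SAP: the protocol commits to particular tests, an entry threshold and a selection procedure, and explains its main model by a matched design that its stated design does not contain.

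A reader might infer that visits will be pooled and that false-positive rates near 17% follow. The documents do not support that: no pooling is stated, no assessment times are given, and the evaluation battery is listed once. A reader might equally infer that repeated visits will be thrown away; that is not stated either. It would also be wrong to fault every named test, since the allele-frequency and Hardy-Weinberg tests are right to use one genotype per child.

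**Conclusion.** The point holds as a mismatch between the declared design and the committed methods. As written, stage-specific frequency and the link from early components to later outcomes, which together make up Hypothesis 1A under Specific Aim 1, have no analysis. This conclusion rests on the text alone and needs no assumption about visits.

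Its numerical size cannot be derived from the protocol. The type I error of 8.6% to 26.6% (2 to 4 records, correlation 0.3 to 0.7) is conditional on pooling records as independent, and applies in full only to exposures fixed within the child. For cumulative dose, which can change during treatment, it is closer to an upper bound.

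It cannot be assumed that the repair needs no new data, because the protocol does not establish that stage-specific records will exist. Nor can the survivors be taken as assessed once, since their cohort is itself called longitudinal. The change should be made; it does not by itself invalidate the single-record genetic tests.

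**What to change.** 1. Define the therapy stages or assessment times for the 400, and say which assessments are repeated at each.
2. Report the frequency of each component and of the syndrome by stage, with confidence intervals.
3. Model these outcomes with logistic GEE (child as cluster, robust standard errors) or a mixed-effects logistic model, with stage as a term. Use a discrete-time hazard model for new onset of the syndrome.
4. Keep the one-record-per-child tests for allele frequencies and Hardy-Weinberg equilibrium.
5. If stage-specific records will not be collected, state the rule that yields one record per child, and withdraw the longitudinal and stage-of-therapy claims.
6. Reconcile the Sample Size entry, which enrols children as treatment begins, with the survivor-only eligibility criteria. The sponsor must settle which population is meant.

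The cost is revised analysis wording, modest extra programming and a written assessment schedule. If assessments by stage are not already planned, collecting them is a further cost that the protocol does not allow one to estimate.

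### Do the survival-time strata leave out survivors 6 to 12 months off therapy, and does the age cap confound them?

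*Protocol*

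**What the plan says.** The Cases paragraph under Evaluation in the Protocol states: "Cases will be stratified by survival time (1-4, 5-9, and" 10 years or more. It does not say whether survival time starts at diagnosis or at the end of therapy, or when a survivor is assigned to a stratum.

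The next paragraph sets entry to the survivor cohort. Survivors must "be 15 years of age or younger, and at least 6 months from the completion of the therapy". Recruitment continues: "Because RPC is a retrospective cohort study with ongoing recruitment (additional survivors become eligible over time". The eligibility list under Study Population repeats the age limit (no more than "15 years of age at time of enrollment") but does not repeat the 6-month rule.

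For Aim 3, Analysis of objectives plans crude odds ratios: "This will be done by univariate conditional logistic regression, to account for the matched design". Model building follows: "Exposures for which the P-value is less than 0.25 in univariate analysis will be entered into a multivariate conditional logistic regression model", and then "Backward stepwise regression procedures will be used to develop the final multivariate model". The matching factors are not named. Neither survival time nor time since therapy appears among the planned comparisons or covariates.

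**The concern.** Three things look wrong on a first reading.

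- **A gap in the strata.** The only clock that the Protocol defines for survivors runs from the end of therapy ("at least 6 months from the completion of the therapy"). On that clock the bands start 6 months later than eligibility. With ongoing recruitment, those 6 months are where newly eligible survivors arrive. They would be dropped from stratified results or placed ad hoc.
- **Confounding built in by the age cap.** A survivor aged 15 or younger who is at least 10 years from diagnosis must have been diagnosed very young. A comparison of metabolic syndrome between strata (Aim 1) would then partly compare ages at treatment.
- **A selection rule that could remove the adjustment.** If age at diagnosis were handled as one of the screened exposures, the univariate screen or the backward steps could drop it from a survivor model that uses time since therapy (Aim 3).

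At stake would be a biased reading of how risk changes with time since treatment, and incomplete coverage of the most recently treated survivors.

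**Working it through.** **Inputs.** From the Protocol: bands of 1–4, 5–9 and at least 10 years; entry from 6 months after therapy; age cap 15. Not given: the origin of survival time, the duration of therapy, and the distributions of age at diagnosis and of enrolment. Where these are needed they are assumed below.

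**1. Do the bands cover every eligible survivor?** Read as completed years, the bands are 12–59, 60–119 and 120 or more months.

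- *From end of therapy:* months 6 to 11 are eligible and fall in no band. From month 12 on, every time is covered.
- *From diagnosis:* earliest survival time = duration of therapy + 6 months. Three months of therapy gives 3 + 6 = 9 months (gap); 6 months gives 6 + 6 = 12 (no gap); 24 months gives 24 + 6 = 30 (no gap).
- *Other readings of the bands, from end of therapy:* if years are numbered from the first, months 6 to 11 belong to year 1; if years are rounded to the nearest whole number, 0.5 to under 1 rounds to 1. Neither leaves a gap.

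The gap therefore needs two choices that the text does not make: end of therapy as origin, and completed years.

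**2. How far does the cap restrict age at diagnosis?** Ceiling = age cap − lower limit of the stratum, less the duration of therapy if the origin is end of therapy (2 years assumed).

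| Origin | Cap | 1–4 years | 5–9 years | ≥10 years |
|---|---|---|---|---|
| Diagnosis | 15.0 | 15 − 1 = 14 | 15 − 5 = 10 | 15 − 10 = 5 |
| Diagnosis | under 16 | under 15 | under 11 | under 6 |
| End of therapy | 15.0 | 15 − 2 − 1 = 12 | 15 − 2 − 5 = 8 | 15 − 2 − 10 = 3 |
| End of therapy | under 16 | under 13 | under 9 | under 4 |

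Only the upper end is cut off. Children diagnosed very young can appear in every stratum, so the ranges overlap and the confounding is partial.

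**3. What size might these effects have?** This is a simulation in which every distribution is assumed: age at diagnosis uniform on 0–16 years or peaked early (gamma, shape 3, scale 1.8); therapy 2 years or uniform on 0.5–2.5 years; time since diagnosis uniform on 0–16 years (even) or exponential with mean 4 years (front-loaded); cap 15 or 16.

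- Without a stratum, from end of therapy: 5.6–7.9% (even) or 13.7–16.6% (front-loaded). From diagnosis: 0%.
- Mean age at diagnosis, ≥10 years against 1–4 years, even enrolment: lower by 2.3–4.3 years (from diagnosis) or 2.7–4.3 years (from end of therapy).
- Mean attained age, same comparison: higher by roughly 4 to 6 years.

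**4. Would holding age at diagnosis fixed isolate time since therapy?** Attained age = age at diagnosis + time since diagnosis. With age at diagnosis fixed, each further year of survival is exactly one further year of attained age. Adjustment would exchange one mixture for another. If sets were matched on attained age in 1-year bands, age at diagnosis and time since therapy would be nearly collinear within sets (r −0.95 to −0.99 under the same assumptions), and only one could sensibly be entered.

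**5. Does a planned analysis depend on the strata?** Analysis of objectives lists descriptive summaries, tests of association with metabolic syndrome, allele frequencies, conditional logistic regression and a biomarker regression. None is specified by survival time.

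**The case for a change.** The best case for a change is that this detail has not simply been left to a later document. The Protocol itself fixes both the bands and the entry rule, and on one natural reading they do not meet. Survival time is the only stratifier it names for survivors, so readers will compare metabolic syndrome across the strata whether or not a test is written. A child diagnosed at 8 can never reach the stratum of 10 years or more before passing the age cap, and the Protocol does not mention this link. Stating the origin would cost a few words.

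Part of this stands. The origin is undefined, the ceilings follow from the cap, and anyone who compares the strata should keep both age at diagnosis and attained age in view.

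The rest is weaker. An undefined origin is not a contradiction, since ordinary readings exist on which everyone has a stratum. Nothing fixes the stratum at enrolment, and in a longitudinal cohort a survivor who enters at 6 months reaches 1 year soon after. A lower ceiling on age at diagnosis with longer survival is a property of any age-capped paediatric cohort. The selection-rule point needs four things that the Protocol does not state: that time since therapy is modelled, that age at diagnosis counts as a screened exposure, that it is not a matching factor, and that selection then drops it.

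**Conclusion.** No change to the plan follows. The gap is a conditional one: it exists only if survival time is counted in completed years from the end of therapy, and it closes from diagnosis for anyone treated for at least 6 months. The origin, the lower limit of the first band and the time of assignment are gaps that analysts can fill sensibly, for example by letting the first band begin where eligibility begins.

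The restriction on age at diagnosis is real (ceilings of 14, 10 and 5 years from diagnosis with the cap at 15.0), but it distorts no analysis that the Protocol specifies, and frequencies within one stratum describe that stratum correctly. Forcing age at diagnosis into a model would leave time since diagnosis fully mixed with attained age. The choice of age term is thus a trade-off for whoever specifies such a comparison, not a clear gain to require now.

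The ceilings from diagnosis rest on the Protocol's own figures. Those from end of therapy also need the assumed 2 years of therapy. The percentages without a stratum and the mean-age differences rest entirely on assumed distributions and only illustrate scale.
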